# 6.7.1.1 Adverse Events of Special Importance(AESI)

Adverse events of peripheral neuropathy may be considered AEs of special importance. Other AEs such as neutropenia may be added to AEs of special importance, as necessary. The definition of adverse events of special importance and search criteria will be maintained in a separate document and will be finalized prior to database lock. AESI will be summarized by MedDRA Preferred Term in descending frequency of occurrence.

# 6.7.2 Clinical Laboratory Parameters

Grading of laboratory values will be assigned programmatically per the NCI CTCAE v4.03. The highest post-baseline grade will be presented for each lab test.

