Even though better efficacy had been observed with 1.5 mg/kg, preliminary results led to 1.25 mg/kg being chosen for further expansion in Study SGNLVA-001 because of the higher frequency of neutropenia experienced at 1.5 mg/kg. Most of the clinically significant neutropenia occurred after 3 weekly doses at the 1.5 mg/kg dose level. These observations suggested that an LV dosing holiday may be needed to mitigate neutropenia.

Pharmacokinetic analysis of relative dosing intensity (RDI) with LV 1.25 mg/kg q1wk in monotherapy also showed that dose intensity started to decrease at Cycle 2, with dosing reduced to 2 doses in every 21-day cycle over time (Seagen data on file). This supports that a drug holiday could be beneficial for long-term treatment. Implementing a drug holiday may mitigate toxicities, reduce the need for dose modification, and therefore improve efficacy. This is further supported by PK simulation which demonstrated that giving LV 1.5 mg/kg on Days 1 and 8 every 21 days resulted in similar drug exposures as that of 1.25 mg/kg q1wk dosing

(Days 1, 8, and 15). Hence, administration of LV 1.5 mg/kg on Days 1 and 8 every 21 days may result in improved efficacy and safety of LV.

Part D will only enroll patients with PD-L1 CPS<10. Pembrolizumab + chemotherapy has received regulatory approval in the 1L advanced TNBC PD-L1 high (CPS≥10) subpopulation based on an overall survival benefit (Schmid 2018; Cortes 2020). Similar benefit was not observed in patients with PD-L1 CPS<10, where the standard of care remains chemotherapy and the outcomes are poor (response rates ~40% and median PFS about 5.5 months). Thus, these patients represent a population that continues to have high unmet medical need. This ongoing SGNLVA-002 study has demonstrated that LV + pembrolizumab not only is active against mTNBC but also can have a manageable safety profile suggesting that LV + pembrolizumab may provide an option for these patients.

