6.2.3. Treatment Period (Day 1 to Day 21)

6.2.3.1. Day 1

For Cycle 1, if baseline visit activities occur within 1 day prior to Day 1, the following assessments do not need to be repeated. For Cycle 2 and beyond, these assessments have a window of -2 days:

- Physical examination (see Section 7.5.4)
- Weight
- ECOG performance status (see Appendix F)
- Serum chemistry panel (detailed in Section 7.5.3) to be evaluated prior to infusion.
 Hold dose if blood glucose level is >250 mg/dL.
- CBC with differential (detailed in Section 7.5.3) to be evaluated prior to infusion.
- Pregnancy test (for patients of childbearing potential; performed locally; does not need to be repeated if performed within 3 days of Day 1)
- Thyroid function tests (detailed in Section 7.5.3; to include TSH, T3 or free T3, and free T4). Day 1 of each odd-numbered cycle only (i.e. Cycles 1, 3, 5, 7, etc.)

The following procedures must be performed on Day 1 of every cycle:

- Vital signs (within 60 minutes prior to LV infusion, within 60 minutes prior to pembrolizumab infusion, within 2 hours of ending each infusion, and during infusion/s as clinically indicated (See Section 7.5.2)
- Predose blood samples for biomarkers (Cycle 1 only). See time points in Appendix E.
- Predose blood samples for PK (Cycle 1 only). See time points in Appendix B.
- Post dose blood samples for PK (Cycle 1 only). See time points in Appendix B.
- Predose blood samples for ATA (Cycle 1 only). See time points in Appendix B.
- LV infusion (if dosing criteria in Section 5.2.3.5 are met)
- Pembrolizumab infusion
- Collection of concomitant medication information
- Collection of AEs

6.2.3.2. Day 3 (Part B Cycle 1 required for patients in US sites, optional for patients outside US sites; window: Days 3-4)

Blood samples for PK

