6.2.3.4. Day 8 (Cycles 1-2 only; ±2 days)

- CBC with differential (detailed in Section 7.5.3)
- Serum chemistry panel (detailed in Section 7.5.3)
- Collection of concomitant medication information
- Collection of AEs
- Cycle 1 only:
 - Blood samples for PK

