6.2.3.5. Day 15 (Cycle 1 only; ±2 days)

- Fresh tumor biopsy only for patients enrolled in Part B (window: Days 15–21)
- Blood samples for PK
- Collection of concomitant medication information
- Collection of AEs

6.3. Parts C (q1wk LV dosing) and D (Days 1 and 8 LV dosing)

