- O At least 7 days must elapse between administrations of LV. Hold dose if dosing criteria outline in Section 5.2.3.5 are not met.
- P For Cycle 2 and beyond, may be performed up to 2 days prior to Day 1.
- Q Laboratory assessments are to be performed locally and results are to be submitted to the central laboratory (with the exception of pregnancy testing); detailed in Section 7.5.3.
- R Cycles 1 and 2 only.
- S Part C only.
- T In Part D only, archival or freshly obtained tumor tissue will be used to determine eligibility based on PD-L1 CPS<10 status as determined locally by a PD-L1 IHC assay using the 22C3 clone.
- U Cycles 1 and 2 only for Part D and every cycle for Part C.
- V Follow-up will occur every 6 weeks (±1 weeks) 30 days post last treatment for patients on LV only and 90 days for those on pembrolizumab.

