#### 5 STATISTICAL CONSIDERATIONS

# 5.1 General Principles

Descriptive statistics (mean, median, standard deviation, minimum, and maximum) will be summarize continuous variables, Frequencies and percentages will be used to summarize categorical variables. The two-sided 95% exact confidence interval using Clopper-Pearson methodology (Clopper 1934) will be calculated for the response rates where applicable (e.g., ORR).

The median survival time will be estimated using the Kaplan-Meier method; the associated 95% confidence interval (CI) will be calculated based on the complementary log-log transformation (Collett 1994).

Unless otherwise specified, data are to be summarized by dose level and overall. DLT analysis will only include patients in Part A and Part C dose finding part.

Any analysis not described in this plan will be considered exploratory, and will be documented in the clinical study report (CSR) as a post hoc analysis or a change to the planned analysis.

To comply with regulatory electronic submission guidelines, listings of all clinical data will be submitted as electronic data sets. To facilitate data review for the study report, only pertinent data listings will be created and attached to the appendix of the CSR. All statistical tables, listings, and figures will be produced using SAS, version 9.3 or more recent. Other statistical software, if used, will be described in the CSR.

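### The planned worst-grade laboratory table spans parts with different CBC frequency; Parts C and D need an added table on their identical weekly draws

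*SAP*

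**What the plan says.** SAP 6.7.2 grades laboratory values by program and then states: "The highest post-baseline grade will be presented for each lab test". It sets no restriction to particular visits and plans no summary by cycle and no count of samples. SAP 5.1 supplies the grouping: "Unless otherwise specified, data are to be summarized by dose level and overall". The starting doses separate the schedules: 2.0 and 2.5 mg/kg every 3 weeks in Parts A and B, 1.0 and 1.25 mg/kg weekly in Part C, and 1.5 mg/kg on Days 1 and 8 in Part D.

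The CBC schedule in the current protocol differs by part:

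- **Parts A and B (Section 6.2.3).** On Day 1 of every cycle: "CBC with differential (detailed in Section 7.5.3) to be evaluated prior to infusion". The only other CBC visit is headed "Day 8 (Cycles 1-2 only; ±2 days". The Day 15 visit lists biopsy, PK, concomitant medications and AEs, but no CBC.
- **Parts C and D (Section 6.3.3).** Both have a CBC on Days 1 and 8 of every cycle. For Day 15, Appendix C footnote U says: "Cycles 1 and 2 only for Part D and every cycle for Part C".

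Laboratory abnormalities are a primary safety endpoint (SAP Section 2). The protocol synopsis makes the recommended dose and schedule a primary objective. Protocol 3.2.3.4 gives neutropenia as one reason for the Part D schedule: "These observations suggested that an LV dosing holiday may be needed to mitigate neutropenia".

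**The concern.** A maximum taken over more samples can only stay the same or rise. Two groups with the same true neutropenia will therefore show different worst-grade rates if one is sampled more often. In this trial the sampling difference follows the schedule, and the schedule is part of what the trial is meant to choose.

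The sharpest case is C against D. From Cycle 3, Part D drops the Day 15 draw, one week after its second dose, while Part C keeps it. This detection difference points the same way as the off-week rationale. Nothing in SAP 6.7.2 would let a reader separate less neutropenia from fewer draws.

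**Working it through.** The plan states no figure on this point to reproduce. The check counts scheduled draws and asks what the spacing does to detection.

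**Step 1. Draws per cycle and longest gap from Cycle 3** (Protocol 6.2.3, 6.3.3, Appendix C)

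| | A/B | C | D |
|---|---|---|---|
| CBC days from Cycle 3 | 1 | 1, 8, 15 | 1, 8 |
| CBCs per cycle | 1 | 3 | 2 |
| Gaps (days) | 21 | 7, 7, 7 | 7, 14 |
| Longest gap (days) | 21 | 7 | 14 |

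**Step 2. Post-baseline draws over 8 cycles** (Cycle 1 Day 1 is pre-dose and excluded; the end-of-treatment CBC is the same in every part and left out)

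- A/B: Cycle 1 Day 8, Cycle 2 Days 1 and 8, then Day 1 of Cycles 3 to 8 = 1 + 2 + 6 = 9
- C: 3 × 8 − 1 = 23
- D: 2 + 3 + 6 × 2 = 17

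The C–D difference of 6 is the Day 15 draw in Cycles 3 to 8.

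**Step 3. Chance that a scheduled draw falls within an episode**

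Assume one episode lasting d days, with onset uniform over a 21-day cycle. The documents give no duration, so d runs from 3 to 7.

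Detection = Σ min(gap, d) / 21

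For d = 5 from Cycle 3: A/B 5/21 = 24%; C (5 + 5 + 5)/21 = 71%; D (5 + 5)/21 = 48%.

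| d (days) | A/B | C | D |
|---|---|---|---|
| 3 | 14% | 43% | 29% |
| 5 | 24% | 71% | 48% |
| 7 | 33% | 100% | 67% |

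With an assumed true rate of 20% in every part and d = 5, the observed rates would be 0.20 × 0.71 = 14% in C, 0.20 × 0.48 = 10% in D and 0.20 × 0.24 = 5% in A/B. The A/B column applies only to patients sampled under the current schedule.

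In Cycles 1 and 2, C and D are both weekly, so their detection is equal. A/B then has gaps of 7 and 14 days: for d = 5, 10/21 = 48% against 71%.

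**Step 4. Draws the parts share**

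- C and D: Cycle 1 Days 8 and 15; Cycle 2 Days 1, 8 and 15; Cycle 3 Day 1. That is six draws, weekly in both parts.
- All parts: Cycle 1 Day 8; Cycle 2 Days 1 and 8; Cycle 3 Day 1. That is four draws.

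**Step 5. Time since last LV dose at the four draws common to all parts** (no delays)

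| Draw | A/B | C | D |
|---|---|---|---|
| Day 8 of Cycles 1 and 2 | 7 days | 7 days | 7 days |
| Day 1 of Cycles 2 and 3 | 21 days | 7 days | 14 days |

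Matching on calendar day therefore equalises the number of draws for A/B, but not where they fall after dosing. A/B also has no Day 15 draw to fill the gap. For C and D the six draws are a complete weekly series, so the 7 against 14 days at Day 1 reflects the regimens and not the sampling.

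**The case against.** **A/B sampling.** The current schedule does not describe every A/B patient. The change history shows that Day 8 and Day 15 safety draws were at one stage required in Cycles 1 to 4. They were cut to Day 8 of Cycles 1 and 2 only with the amendment that added Part B Cohort 2. On the earlier pattern the 8-cycle count is 2 + 9 + 4 = 15, not 9. By then Part A had been run and 2.5 mg/kg was already under evaluation in Cohort 1 (Protocol 3.2.3.1). This stands: the A/B gap is smaller for those patients, and the documents do not say how many there were.

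**C against D.** The two differ by one draw per cycle, and only from Cycle 3. In the earlier monotherapy study, most clinically significant neutropenia at 1.5 mg/kg followed three weekly doses. Part C's Day 15 sample is taken before its third dose. The documents therefore do not show that the dropped draw is where events would be found. This stands as a limit on size. It does not make the detection equal.

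**Other information.** No hypothesis test is planned (SAP 5.7). SAP 6.7.1 tabulates Grade 3–5 AEs, dose delays and dose reductions. Protocol 9.3.9.4 allows laboratory summaries by visit. These soften the consequence. However, SAP 6.7.2 does not take up the by-visit option, and the AE tables depend partly on the same draws: a low count that interrupts treatment can become an AE (Protocol 7.5.1.1), and the within-cycle neutrophil check falls on Days 8 and 15 in C but only Day 8 in D (Section 5.2.3.5).

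**Stronger readings.** A reader might infer that sampling alone will rank A/B lowest, then D, then C, and so falsely confirm the off-week hypothesis. The documents do not support that. G-CSF rules, neutrophil-based holds and the Part D PD-L1 restriction also differ by part, unscheduled draws recover some episodes, and Part D was also opened for activity in a PD-L1 CPS <10 population. Nor does the full bias carry over to AE terms, because a laboratory value alone is generally not recorded as an AE.

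**Conclusion.** The concern holds in a limited form. From Cycle 3, at equal true risk, the planned table would detect worst-grade neutropenia less often in Part D than in Part C, by roughly a third for episodes of 3 to 7 days (29% against 43%, 48% against 71%, 67% against 100%). It would also detect it less often in A/B than in C, by an amount the documents do not allow anyone to compute.

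The direction rests on the schedules and on the nature of a maximum. The percentages rest on assumed episode duration, random onset and scheduled draws only. The net observed difference between parts will reflect more than sampling.

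This is a cheap improvement to the reporting. It is not a flaw that undermines the trial.

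**What to change.** In SAP 6.7.2:

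1. Add a worst-grade hematology table for Parts C and D restricted to Cycle 1 Days 8 and 15, Cycle 2 Days 1, 8 and 15, and Cycle 3 Day 1. Base any C-versus-D statement about laboratory neutropenia on it, read alongside the all-draws table.
2. Add a supportive table for all parts on Cycle 1 Day 8, Cycle 2 Days 1 and 8, and Cycle 3 Day 1. Note that time since the last LV dose differs by schedule and that G-CSF rules and population also differ.
3. Report the number of CBCs per patient by part, which will also show the denser earlier sampling in A/B.
4. Footnote the all-draws table as not directly comparable across schedules.

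The cost is one or two tables from data already collected. The downside is that late-cycle events appear only in the all-draws table, so that table stays. Clinical monitoring is unaffected.

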recent/fresh tissue if it was collected after completion of the patient's most recent cytotoxic therapy. If neither is available, please discuss with medical monitor.

- The following baseline laboratory data:
 - absolute neutrophil count ≥1,500/µL
 - platelet count ≥100,000/µL
 - hemoglobin ≥8.0 g/dL
 - serum bilirubin ≤1.5x upper limit of normal (ULN) or ≤3x ULN for patients with Gilbert's disease
 - serum creatinine ≤1.5x ULN OR glomerular filtration rate (GFR) ≥60 mL/min/1.73 m² for patient with creatinine levels >1.5x institutional ULN. GFR calculation is found in Appendix N.
 - Alanine aminotransferase (ALT) and aspartate aminotransferase (AST) ≤1.5x ULN or ≤3x ULN if liver metastases are present
 - International normalized ratio (INR) or prothrombin time (PT) ≤1.5x ULN unless subject is receiving anticoagulant therapy as long as PT or partial thromboplastin time (PTT) is within therapeutic range of intended use of anticoagulants
 - Activated partial thromboplastin time (aPTT) ≤1.5x ULN unless subject is receiving anticoagulant therapy as long as PT or PTT is within therapeutic range of intended use of anticoagulants
- For patients of childbearing potential as defined in Section 4.3, the following stipulations apply:
 - a. Must have a negative serum or urine pregnancy test (minimum sensitivity 25 mIU/mL or equivalent units of beta human chorionic gonadotropin [β-hCG]) result within 3 days prior to the first dose of LV/pembrolizumab. Patients with false positive results and documented verification that the patient is not pregnant are eligible for participation.
 - b. Must agree not to try to become pregnant from the time of enrollment until at least 6 months after the final dose of study drug. If heterosexually active, must consistently use 2 highly effective methods of birth control (as defined in Appendix G) during this time period.
 - c. Must agree not to breastfeed or donate ova, starting at time of informed consent and continuing through 6 months after the final dose of study drug administration.
- 10. Male patients under the following conditions:
 - a. Must agree not to donate sperm starting at time of informed consent and continuing throughout the study period and for at least 6 months after the final study drug administration.

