5.7. Management of Hyperglycemia

Investigators should monitor blood glucose levels and are advised to perform additional assessments if any symptoms of hyperglycemia are observed, including a thorough evaluation for infection. In addition, if steroids are used to treat any other condition, blood glucose levels may require additional monitoring. If elevated blood glucose levels are observed, patients should be treated according to local standard of care and referral to endocrinology may be considered.

Patients, especially those with a history of or ongoing diabetes mellitus or hyperglycemia, should be advised to immediately notify their physician if their glucose levels become difficult to control or if they experience symptoms suggestive of hyperglycemia such as frequent urination, increased thirst, blurred vision, fatigue, and headache.

Patients who enter the study with elevated hemoglobin A1c (HbA1c) (≥6.5%) or fasting glucose (≥126 mg/dL or ≥7.0 mmol/L) at screening should receive glucose management prior to or within 1 week of starting study treatment.

In Part A and B, blood glucose should be checked prior to each dosing and dose should be withheld for blood glucose >250 mg/dL or >13.9 mmol/L, testing may be repeated on the same day of dosing. LV dose may be delivered on the same day once the patient's blood glucose has improved to ≤250 mg/dL or ≤13.9 mmol/L and the patient is clinically and metabolically stable.

In Part C, blood glucose may be checked on Day 8 and Day 15 by fingerstick as indicated, particularly in patients at risk for hyperglycemia. Day 8 and 15 dosing with LV should be withheld for blood glucose >250 mg/dL or >13.9 mmol/L. Testing may be repeated on the day of dosing. LV dose may be delivered on the same day once the patient's blood glucose has improved to ≤250 mg/dL or ≤13.9 mmol/L and the patient is clinically and metabolically stable.

In Part D, blood glucose may be checked on Day 8 by fingerstick as indicated, particularly in patients at risk for hyperglycemia. Day 8 dosing with LV should be withheld for blood glucose >250 mg/dL or >13.9 mmol/L. Testing may be repeated on the day of dosing. LV dose may be delivered on the same day once the patient's blood glucose has improved to ≤250 mg/dL or ≤13.9 mmol/L and the patient is clinically and metabolically stable.

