7.5.1. Adverse Events

7.5.1.1. Definitions

Adverse Event

According to the International Council for Harmonisation (ICH) E2A guideline Definitions and Standards for Expedited Reporting, and 21 CFR 312.32, investigational new drug (IND) Safety Reporting, an AE is any untoward medical occurrence in a patient or clinical investigational subject administered a medicinal product and which does not necessarily have a causal relationship with this treatment.

The following information should be considered when determining whether or not to record a test result, medical condition, or other incident on the Adverse Events and Pre-existing Conditions CRF:

- All study protocol-related AEs that occur after the consent form is signed but before treatment allocation must be reported by the investigator.
- All medical conditions present or ongoing predose on study Day 1 should be recorded.
- All AEs (regardless of relationship to study drug) should be recorded from study Day 1
 through the end of the safety reporting period (see Section 6). Complications that occur in
 association with any procedure (e.g., biopsy) should be recorded as AEs whether or not
 the procedure was protocol mandated.

- Changes in medical conditions and AEs, including changes in severity, frequency, or character, during the safety reporting period should be recorded.
- In general, an abnormal laboratory value should not be recorded as an AE unless it is
 associated with clinical signs or symptoms, requires an intervention, results in a SAE, or
 results in study termination or interruption/discontinuation of study treatment. When
 recording an AE resulting from a laboratory abnormality, the resulting medical condition
 rather than the abnormality itself should be recorded (e.g., record "anemia" rather than
 "low hemoglobin").

Serious Adverse Events

An AE should be classified as an SAE if it meets one of the following criteria:

Fatal:	AE resulted in death
Life threatening:	The AEs placed the patient at immediate risk of death. This classification does not apply to an AE that hypothetically might cause death if it were more severe.

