9.3.9.4. Clinical Laboratory Results

Laboratory values (e.g., chemistry, hematology, and pulmonary function tests) may be presented graphically by visit. Summary statistics may be tabulated as appropriate by scheduled visit. Laboratory values will be listed with grade per NCI CTCAE v4.03 and flagged when values are outside the normal reference range.

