#### 2 OBJECTIVES AND ENDPOINTS

Primary Safety Objectives	Corresponding Endpoint

 
Assess the safety and tolerability of the combination of SGN-LIV1A and pembrolizumab in patients with LA/M TNBC
 
Identify the recommended dose of SGN-LIV1A in combination with pembrolizumab in patients with LA/M TNBC
 
	Type, incidence, severity, seriousness, and relatedness of AEs     Laboratory abnormalities     Incidence of dose-limiting toxicity (DLT)
Primary Efficacy Objective	Corresponding Endpoint
Evaluate the confirmed ORR of the combination of SGN-LIV1A and pembrolizumab in patients with LA/M TNBC	Confirmed ORR as determined by the investigator according to RECIST v1.1
Secondary Efficacy Objectives	Corresponding Endpoints
Evaluate the DOR, DCR, PFS, and OS	DOR as determined by RECIST v1.1     DCR as determined by RECIST v1.1     PFS as determined by RECIST v1.1     OS
Exploratory Efficacy Objectives	Corresponding Endpoints

Evaluate the ORR, DOR, DCR, and PFS according to iRECIST	ORR as determined by iRECIST  DOR as determined by iRECIST  DOR as determined by iRECIST  PFS as determined by iRECIST
Pharmacokinetic and Immunogenicity Objectives	Corresponding Endpoints
Assess PK and incidence of antitherapeutic antibodies (ATAs) of SGN-LIV1A	Selected PK parameters for SGN-LIV1A, and MMAE     Incidence of ATAs to SGN-LIV1A
Biomarkers Objectives	Corresponding Endpoints
Evaluate PD-L1 and LIV-1 expression-response relationship     Assess exploratory biomarkers (e.g., in the tumor immune microenvironment or periphery) of study treatmentmediated pharmacodynamic effects	PD-L1 and LIV-1 expression-response relationship following treatment with SGN- LIV1A and pembrolizumab     Relationship between biomarkers in blood and tumor tissue to efficacy, safety, or other biomarker endpoints following treatment with SGN-LIV1A/pembrolizumab

RECIST = Response Evaluation Criteria in Solid Tumors; iRECIST = immune-related RECIST.

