# Appendix C Definition of the Term "Treatment-Emergent" with Respect to AE Classification

The algorithm below should be used to determine whether an adverse event (AE) is classified as a treatment-emergent adverse event (TEAE). A TEAE is defined as any AE which worsens in severity during the safety reporting period or is newly occurring at any time, where newly occurring means that the AE was not present at baseline. For ease of reading, both pre-existing conditions and AEs will be referred to as AEs for the remainder of this document. AE dates should be imputed in accordance with the algorithm detailed in Appendix A prior to determination of TEAE classification. Details of the TEAE classification are as follows:

- For each patient, determine the first dose date, which is the earliest date the patient receives any amount of study drug.
- Baseline AEs: classify an AE record as baseline AE if it satisfies both criteria a and b below:

AE onset satisfies either of i, ii or iii below:

- Onset date is prior to the first dose date
- ii. Onset date is the same as the first dose date, and Onset Period is "started after consent but before the first dose of any study treatment" or Onset Time Relative to Study Treatment is "started before first infusion or before infusion on any dosing day"
- iii. Onset Period is "started before the signing of consent" or "started after consent but before the first dose of any study treatment"

AE end date satisfies either of i or ii below:

- End date is the same as or after the first dose date
- End date is missing with outcome equal to

recovering/resolving, or

not recovered/not resolved, or

unknown or missing

- Post-baseline AEs: classify an AE record as post-baseline AE if it meets either of criteria a, b or c below:
  - a Onset date is after the first dose date
  - b Onset date is the same as the first dose date, and Onset Period is "started after the first dose of any study treatment" or Onset Time Relative to Study Treatment is not "started before first infusion or before infusion on any dosing day"
  - c Onset Period is "started after the first dose of any study treatment"
- TEAE flag will be derived as follows:
  - For all AE records that have an end date prior to the first dose date, assign TEAE flag to 'N'
  - For all baseline AEs, assign TEAE flag to 'N'
  - c. For post-baseline AEs:
    - If the post-baseline AE is a continuing event of a baseline AE (i.e., events with

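### The only committed general summary of graded laboratory values is the worst post-baseline grade with no baseline reference, so abnormalities carried in from entry are counted with new ones

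*SAP*

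**What the plan says.** SAP 2 and Protocol 2 list "Laboratory abnormalities" as an endpoint for the primary safety objectives. SAP 6.7.2 is two sentences long: grades are assigned by program under CTCAE v4.03, and "The highest post-baseline grade will be presented for each lab test". SAP 5.1 has outputs produced by dose level and overall. SAP 5.4.1 defines baseline as the last non-missing value before first dose, but 6.7.2 does not use it.

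Protocol 9.3.9.4 adds a listing ("Laboratory values will be listed with grade per NCI CTCAE v4.03 and flagged when values are outside the normal reference range") and optional output: graphs by visit, and "Summary statistics may be tabulated as appropriate by scheduled visit". SAP 6.7.5 summarises four liver tests and the patients whose post-baseline results fit Hy's law.

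On entry values, Protocol 4.1 accepts "Alanine aminotransferase (ALT) and aspartate aminotransferase (AST) ≤1.5x ULN or ≤3x ULN if liver metastases are present". It also accepts hemoglobin down to 8.0 g/dL, and bilirubin up to 1.5 times ULN (3 times only in Gilbert's disease). Under Protocol 5.7, "Patients who enter the study with elevated hemoglobin A1c (HbA1c) (≥6.5%) or fasting glucose" above the stated cut-off are given glucose management and are not excluded.

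Adverse events do refer to baseline. In SAP Appendix C, "newly occurring means that the AE was not present at baseline".

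**The concern.** A patient whose abnormal value is the same before and after first dose appears in the SAP 6.7.2 table exactly as a patient whose value became abnormal on treatment. The any-grade rate therefore mixes disease and comorbidity at entry with what happened on ladiratuzumab vedotin (LV) plus pembrolizumab.

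This matters because a primary objective is to identify the dose and schedule. The columns placed side by side come from parts enrolled one after another, Part D has its own PD-L1 criterion, and no covariate adjustment is planned (SAP 5.9). If the share with, say, liver metastases or diabetes differs between cohorts, the laboratory rates differ even when the drug effect does not.

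**Working it through.** **No figure in the plan to reproduce.** The plan states no number on this point. The check is a comparison of passages, followed by an illustration.

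**Which tests are bounded at entry.**
- Bounded: neutrophils, platelets, hemoglobin, bilirubin, ALT and AST have limits in Protocol 4.1. The LV dosing criteria in Protocol 5.2.3.5 also require, on Day 1, neutrophils of at least 1000/µL (which that section equates with Grade 2 or lower), AST, ALT and bilirubin at Grade 2 or lower, and glucose of at most 250 mg/dL. Grade 3 or higher neutropenia, transaminases or bilirubin should therefore not be carried in. For these tests the effect falls mainly on lower grades.
- Not bounded: phosphorus, amylase, lipase and uric acid are on the chemistry panel (Protocol 7.5.3) but have no entry limit in Protocol 4.1. Phosphate is a relevant test: Protocol 3.2.3.2 reports Grade 3 or higher hypophosphataemia in 11.5% of patients on weekly LV 1.25 mg/kg in SGNLVA-001.

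**Size: illustration with every input assumed.** Let
- b = share abnormal at entry
- t = onset rate among patients normal at entry
- w = share of entry-abnormal patients who worsen
- r = share of the remaining entry-abnormal patients with any abnormal result after baseline

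The planned table shows T = (1−b)t + b[w + (1−w)r].
A new-or-worsened count over all treated patients shows E = (1−b)t + bw.

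Take t = 20%, and compare b = 10% with b = 30%.

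| Quantity | b = 10% | b = 30% | Difference |
|---|---|---|---|
| T, full persistence (r = 1, any w) | 0.18 + 0.10 = 28% | 0.14 + 0.30 = 44% | 16 points |
| T, r = 0.5, w = 20% | 0.18 + 0.10×0.60 = 24% | 0.14 + 0.30×0.60 = 32% | 8 points |
| T, r = 0.5, w = 0 | 0.18 + 0.05 = 23% | 0.14 + 0.15 = 29% | 6 points |
| E, w = 0 | 18% | 14% | −4 points |
| E, w = 20% | 20% | 20% | 0 |
| Onset among patients normal at entry | 20% | 20% | 0 |

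In Part D (40 patients), full persistence without worsening puts 40 × 0.10 = 4 or 40 × 0.30 = 12 unchanged patients into the count.

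Two points follow. First, r is the share with at least one abnormal post-baseline result, because the table takes the worst value; the abnormality need not last. Second, E over all treated patients also varies with b unless w equals t. A simple worsening count would not remove the dependence on baseline mix. Conditioning on baseline grade does.

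**The case against.** The strongest reply is that this table does not stand alone, and that the affected counts are mostly minor.

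- A reader might infer that the table is the only record of laboratory changes. It is not: the graded listing, the liver summary and the electronic datasets (SAP 5.1) all exist. But a listing is not a summary, the liver section covers four tests, and none of these is a committed grade comparison with baseline.
- A reader might infer that asymptomatic changes never become adverse events. Protocol 7.5.1.1 is narrower. In general "an abnormal laboratory value should not be recorded as an AE unless it is" linked to signs or symptoms, needs an intervention, leads to an SAE, or ends or interrupts study participation or treatment. A value that holds a dose under Protocol 5.2.3.5 can therefore reach the adverse event tables. Changes without such a consequence generally do not.
- The contrast with adverse events is not absolute. Appendix C also flags a continuing baseline event as treatment-emergent if it is judged treatment-related, with no rise in grade.
- The SAP says post-baseline grade, not toxicity, and plans no hypothesis testing (SAP 5.7). Comparisons across dose levels are informal.
- Raised glucose is to be managed before or within a week of starting treatment, so some entry abnormalities will resolve.
- The move to an abbreviated report (SAP 8.2) explains dropping vital signs, ECG and ECOG-by-visit output. It does not explain why a retained primary endpoint has no baseline reference.

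All of this limits the size of the problem. None of it supplies the missing comparison.

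**Conclusion.** The point stands in a limited form. SAP 6.7.2 counts an entry abnormality seen again after baseline the same as a new one, in the only committed general summary of graded laboratory values, and rates by dose level therefore depend partly on baseline mix.

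The actual size is unknown, because the documents give no baseline prevalence, onset rate or persistence. With 20% onset among patients normal at entry, and 10% against 30% abnormal at entry, the spurious gap is 16 points under full persistence and 6 to 8 points if half persist. It shrinks further as fewer persist.

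The documents do not support reading this as inflated Grade 3 or higher rates across the board. For the tests limited in Protocol 4.1 the distortion is mainly in lower grades; only tests without an entry limit lack that bound. Nor should 20% in the illustration be read as the true rate over all treated patients. It is the rate among those normal at entry.

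**What to change.** In SAP 6.7.2, for each test and dose level:

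1. Add a shift table of baseline grade (SAP 5.4.1 definition) by worst post-baseline grade within the treatment-emergent window of SAP 6.7.1.
2. Report the number worsening to Grade 3 or higher among patients below Grade 3 at baseline.
3. Give any new-or-worsened rate by baseline grade or among patients at risk, not only over all treated patients.
4. Keep the existing worst-grade output alongside.

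The data are already collected, so the cost is modest programming and a short SAP amendment before database lock. Left out of the SAP, the same table would count as exploratory under SAP 5.1.
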